The treatment of SIBO frequently consists of antibiotic therapy. Rifaximin is a poorly absorbed antibiotic with bacteriocidal activity against enteropathogens and is widely prescribed for the treatment of SIBO.³ Nevertheless, both patients and practitioners frequently turn to complementary and alternative medicine, due to the adverse effects associated with antibiotic use and the recurrent nature of SIBO. In 2014, a retrospective study (Chedid et al.) found that the efficacy of a particular herbal therapy was comparable to Rifaximin treatment.³ However, both treatment

options demonstrated a response rate of less than 50%. This investigation will test a more comprehensive, supplement-based therapy in hopes of achieving a greater response rate.

Objectives

This investigation aims to determine the efficacy of a supplement protocol in combination with a low FODMAP diet for the treatment of small intestinal bacterial overgrowth (SIBO).

Patient Selection

Patients diagnosed with SIBO at [name] clinic will be offered the opportunity to enroll in this study as a theoretical treatment option for SIBO. Other treatment options will be discussed with the patient. Enrolled patients must satisfy the following inclusion and exclusion criteria:

Inclusion criteria: A positive diagnosis of SIBO, which will be defined by 1) presentation of the aforementioned symptoms and 2) positive results of a lactulose breath test. Positive breath test results will be defined as an increase in hydrogen of 20 ppm or more and/or an increase in methane of 12 ppm or more compared to baseline by 90 minutes.

Exclusion criteria: 1) Use of prescription antibiotics or antifungals within the past 4 weeks. 2) Younger than 18 or older than 85 years of age 3) Pregnant or breast-feeding 4) Major drug-supplement interactions between essential medication and the proposed supplement therapy. 5) A known allergy to one or more of the ingredients in the supplement therapy. 6) Has been diagnosed and treated for SIBO within the past 6 months. 7) Has undergone a colonoscopy or barium enema within the past 4 weeks. 8) Has an allergy to lactulose. 9) Has diabetes mellitus.

Study Procedures

The supplement protocol is designed to take 8 weeks. Due to the delay in receiving and interpreting test results, the investigation, in its entirety, is estimated to take 12 weeks.

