Visit -1 [name] will assess patient history and symptoms, at his facility in Oxford, Ohio. If suggestive of SIBO, a lactulose breath test will be prescribed. Additional testing may be performed, at the discretion of [name], to aid in the initial diagnosis of the patient.

Visit 0 [name] will assess the results of the breath test and confirm or deny the diagnosis of SIBO. Treatment options for SIBO will be discussed, and the patient will be made aware of this investigation as a theoretical treatment option. Patient eligibility will be determined by [name] who will complete the Patient Eligibility Checklist (Appendix A) for each patient. All female patients will be asked to complete a urine pregnancy test to confirm pregnancy status. Eligible patients will be asked to review

and sign the Informed Consent document. [name] (Medical Assistant at Good Medicine) will be available to discuss patient consent and confidentiality. Enrolled patients will be asked to complete a baseline Medical Symptom Questionnaire (Appendix B). Afterwards, [name] will review the supplement therapy (Supplement Overview - Appendix C) and low FODMAP diet (Low FODMAP Handout - Appendix D). Patients will then be provided with all supplements necessary to complete the investigation. Patients will be asked to discontinue all other supplements during the study. However, no wash out period is required. Prescription medications, over-the-counter medications and/or supplements deemed medically necessary by the patient's primary care physician and/or [name] may be continued, if there are no known contraindications.

Visit 1 Visit 1 will occur approximately 4 weeks after the patient begins the supplement protocol. Patients will be asked to report their compliancy with the supplement protocol and low FODMAP diet and describe adverse effects. Patients will also be asked to complete the Medical Symptom Questionnaire. Patients will be provided with the second lactulose breath test kit and instructed to perform the test within 2 weeks of completing the supplement therapy.

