Any changes to the protocol will be submitted to the IRB for review and approval before implementation. However, a protocol change intended to eliminate an apparent immediate hazard to patients will be implemented immediately. The reviewing IRB will be notified within 10 working days, if an immediate protocol change is necessitated.

The principle investigator ([name]) will provide each patient with full and adequate verbal and written information using the IRB approved informed consent documentation, including the objective and procedures of the study as well as the possible risks involved before inclusion in the study. Informed consent will be obtained prior to performing any study-related procedures, including screening and changes in medications including any washout of medications. A copy of the signed informed consent will be given to the study patient.

Confidentiality

Study-related records identifying the patient will be kept confidential and, to the extent permitted by applicable laws and/or regulations, will not be made publicly available. The IRB and/or other regulatory authorities will have access to study related medical records upon request. Subsequent use of the collected data will exclude patient identifying information.

Intended Use of the Data

The data collected from this investigation will be used to determine the efficacy of the proposed supplement therapy. If efficacious, the results will be distributed in print and digital advertising.

References

4. Reynolds K. Small Intestinal Bacterial Overgrowth: A Case-Based Review. *Journal of Patient-Centered Research and Reviews*. 2015; 2(4): 165-171.
5. Saad R and Chey W. Breath Testing for Small Intestinal Bacterial Overgrowth: Maximizing Test Accuracy. *Perspectives in Clinical Gastroenterology and Hepatology*. 2014; 12:1964-1972.

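### Visit 0 places the eligibility checklist and a urine pregnancy test ahead of consent, which contradicts the protocol's own rule that consent precedes screening

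*Protocol*

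**What the plan says.** Two parts of the protocol set the timing of consent.

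- **IRB Review/Ethics/Informed Consent:** "Informed consent will be obtained prior to performing any study-related procedures, including screening". Screening is named, and no exception is given.
- **Study Procedures, Visit 0:** After the breath test has been reviewed and treatment options discussed, eligibility is determined by the clinician, "who will complete the Patient Eligibility Checklist (Appendix A) for each patient". The next sentence reads: "All female patients will be asked to complete a urine pregnancy test to confirm pregnancy status". Consent follows: "Eligible patients will be asked to review" "and sign the Informed Consent document". The baseline questionnaire, the supplement and diet instruction and the dispensing come after that.

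Three other places bear on the reading. Patient Selection lists as an exclusion criterion "3) Pregnant or breast-feeding". Appendix A repeats pregnancy and breast-feeding as a checklist item and extends it to plans over the next 4 months. The Study Synopsis calls the diagnosis of SIBO from symptoms and a lactulose breath test standard of care, and offers enrolment to patients who already meet the criteria at diagnosis.

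**The concern.** The ethics section puts consent before screening, and Visit 0 puts screening before consent. Clinic staff working from the Visit 0 text would collect a urine specimen and complete a study form on people who have not yet agreed to take part. Each time, they would depart from a commitment that the same protocol makes while claiming consistency with Good Clinical Practice.

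What is at stake is participant protection and compliance with what the IRB approved. No estimate, test or sample size is involved.

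**Working it through.** No arithmetic decides this point. The check is to set the passages side by side and ask whether one order of events can satisfy both.

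**1. Order under the ethics section.** Consent, then any study-related procedure, with screening included by name.

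**2. Order under Visit 0.** (a) Breath-test review and diagnosis; (b) discussion of options, including this study; (c) eligibility decision and Appendix A; (d) urine pregnancy test for all female patients; (e) consent for eligible patients; (f) baseline questionnaire, instruction and dispensing for enrolled patients.

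**3. Does the order rest only on which sentence comes first?** No. Consent in step (e) is directed to eligible patients. Pregnancy is an exclusion criterion, so eligibility is not settled until pregnancy status is known. Steps (c) and (d) must therefore be finished before (e). The Study Synopsis, which offers enrolment to those who meet the criteria at diagnosis, points the same way.

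**4. Are steps (c) and (d) study-related?** Taking each step before (e):

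| Step | Status in the protocol | Conflict with the ethics section |
|---|---|---|
| Symptom assessment and breath test | Described as standard of care | None |
| Urine pregnancy test | Only stated purpose is to confirm pregnancy status, an exclusion criterion; nowhere called routine care | Firm |
| Appendix A: pregnancy plans, allergy to the supplement ingredients | Specific to eligibility for this study | Firm |
| Appendix A: age, medication, medical history | Clinician may already hold much of this from Visit -1 | Weaker |

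**5. Is there a provision that would reconcile them?** The protocol text describes no waiver, no separate screening consent and no exception for eligibility checks. The consent form itself is not in the copy reviewed, so how it describes screening could not be checked.

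**6. How many patients?** The Study Synopsis estimates 10. If 10 are enrolled and *f* patients fail screening, Visit 0 as written produces 10 + *f* checklists before consent, so at least 10. The number of pregnancy tests before consent lies between 0 and 10 + *f*, depending on how many patients are women and agree to the test. The protocol gives neither *f* nor the number of women.

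**The case against.** The strongest reply is that Visit 0 is loosely worded rather than contradictory. All the steps fall within one visit, after the patient has heard about the study. No word such as *before* or *then* stands between the checklist, the test and consent, although the same paragraph does mark sequence later on. Staff could obtain consent first and still carry out every listed step. Patient Selection requires only that enrolled patients meet the criteria, which is compatible with either order.

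This does not remove the conflict. Staff who obtained consent first would be following the ethics section and departing from Visit 0, because Visit 0 directs consent to patients already found eligible.

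Two further objections stand in part:

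- Appendix A is completed by the clinician, and much of it is history that the diagnostic work-up may already have supplied. Transcribing it is a weak example of a study procedure. This narrows the point but leaves the urine test and the study-specific questions.
- What precedes consent is modest: a form and a non-invasive test that patients are asked to take. The supplements, the diet, the stopping of other supplements and the symptom questionnaires all come after the signature. The pre-treatment breath test, later used as the baseline value, does come earlier, but as standard of care.

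A reader might infer that consent fails altogether, or that the route from diagnosis to enrolment could not be reported. The documents support neither. Consent precedes everything the study gives to patients. Nothing says that data on excluded or declining patients are kept as study data, or that a screening-flow report is planned.

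**Conclusion.** The concern holds as an internal contradiction, wrong as written. The ethics section and Visit 0 give opposite orders for consent and screening, and nothing in the protocol reconciles them. The conflict is firm for the urine pregnancy test and the study-specific Appendix A questions, and weaker for history already known from routine diagnosis.

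It recurs for each patient screened under Visit 0 as written, but its practical extent is limited to steps that precede the interventions. The effect on the efficacy estimate is nil.

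The conclusion assumes that the pregnancy test is not part of this clinic's usual diagnostic care, since the protocol does not say that it is, and that no screening consent exists outside the text reviewed. If either assumption fails, the protocol should say so, because the two sections still disagree as they stand.

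**What to change.** Reconcile the two sections by reordering Visit 0 in an IRB amendment:

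1. Review the standard-of-care breath test, confirm or reject the diagnosis, and discuss treatment options, including this study.
2. Obtain informed consent from diagnosed patients who are interested.
3. Complete Appendix A and the urine pregnancy test.
4. Enrol those who are eligible, then proceed to the baseline questionnaire, instruction and dispensing.

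The sentence that directs consent to eligible patients should be reworded so that it is directed to interested patients with a confirmed diagnosis. The Study Synopsis sentence on who is offered enrolment should be aligned with it.

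If the sponsor prefers to keep some chart review ahead of consent, the ethics section would have to say which items are exempt. The pregnancy test and the study-specific questions would still need to follow consent, or a short screening consent.

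The change touches no treatment, endpoint or sample size. Its cost is the amendment itself and some consent discussions with patients who then fail screening.

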[figure not shown]

Pilot Study: Investigating a Novel Supplement-based Therapy for the Treatment of Small Intestinal Bacterial Overgrowth

[name].
Senior Director, Scientific Affairs at Atrium Innovations

Version #2
May 3, 2017

Study Synopsis

The aim of this pilot study is to determine the efficacy of a supplement protocol combined with a low FODMAP diet for the treatment of small intestinal bacterial overgrowth (SIBO). The study is designed as a prospective, open label investigation, with an estimated sample size of 10 patients.

Patients diagnosed with SIBO by [name] at Good Medicine Clinic (Oxford, Ohio) will be offered the opportunity to enroll in this study, if they satisfy the inclusion and exclusion criteria upon initial diagnosis. No control group will be assigned.

The diagnosis of SIBO will be determined via assessment of clinical symptoms and the results of a lactulose breath test. This diagnosis procedure is, currently, the standard-of-care. After administration of the supplement therapy and adherence to a low FODMAP diet (8 weeks), the lactulose breath test will be repeated and symptoms re-assessed by [name].

The post-treatment lactulose breath test and all supplements in the protocol will be provided free-of-charge to enrolled patients. In addition, enrolled patients will not be billed for the mid-treatment office visit. Patient and/or patient insurance will be responsible for all other expenses, including but not limited to the initial breath test, all other office visits and travel.

Background

Small intestinal bacterial overgrowth (SIBO) is a category of gastrointestinal infection, characterized by an increased concentration ($>100,000$ CFU/mL proximal jejunal fluid) of bacteria in the small intestine.¹ Symptoms of SIBO commonly afflict the gastrointestinal tract and include but are not limited to: abdominal pain, discomfort, bloating, cramping, flatulence, diarrhea, constipation, eructation, and low serum B12.^{3,4}

SIBO is believed to be severely under diagnosed and is associated with numerous comorbid conditions including irritable bowel syndrome, diabetes mellitus and hypothyroidism.^{4,5} Small-bowel aspiration (SBA) or breath tests are used to aid in the diagnosis of SIBO. Due to the cost and invasive nature of SBA, glucose or lactulose breath tests are more commonly performed.

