Visit 2 Visit 2 will occur after the results of the post-treatment breath test are available. [name] will interpret the results of the second breath test, and patients will be asked to complete the Medical Symptom Questionnaire, report compliancy with the supplement protocol and low FODMAP diet, and describe any adverse effects. Further treatment options will be discussed if necessary; follow-up treatment will be outside the scope of this investigation.

Risk/Safety Information

This study presents risk in the form of adverse reactions to ingredients in the supplement therapy. Patient risk will be minimized by excluding patients who may respond poorly to the supplement therapy or testing procedures from the study, i.e., by abiding by the aforementioned patient enrollment exclusion criteria.

Monitoring/Reporting

Patients may report adverse events to Good Medicine during scheduled office visits or by phone during office hours. If serious or life-threatening side effects arise, patients are instructed to call 911. Possible side effects include but are not limited to: diarrhea, constipation, nausea, vomiting, bloating or headache. When necessary, [name] or [name] will communicate with patients outside the office by phone and record adverse events in the patient's confidential files. Medical guidance will be provided as necessary.

Study Oversight

This study will be terminated if one-half or more of enrolled patients withdraw due to adverse events. [name] and [name] (Senior Director, Scientific Affairs at Atrium Innovations) will monitor, determine the need for and facilitate the termination of the study. Direct access to study related data will be made available for monitoring, auditing, IRB review and regulatory inspection.

Data Management

Lactulose breath test scores and completed Medical Symptom Questionnaire will be compared pre- and post-treatment to determine the efficacy of the supplement therapy. The significance of the change in breath test scores will be determined if the final sample size permits such analysis.

IRB Review/Ethics/Informed Consent

This study will be conducted in accordance with the ethical principles that have their origin in the Declaration of Helsinki and that are consistent with Good Clinical Practice and applicable regulatory requirements.

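### Data Management and Intended Use credit the pre/post change to the supplement therapy, although the tested intervention is supplements plus a low FODMAP diet

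*Protocol*

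**What the plan says.** Two sections of the protocol state the aim, and both include the diet. Study Synopsis: "The aim of this pilot study is to determine the efficacy of a supplement protocol combined with a low FODMAP diet". Objectives: "This investigation aims to determine the efficacy of a supplement protocol in combination with a low FODMAP diet". The Synopsis also says that the study is open label, has no control group and expects about 10 patients.

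Two later sections state what the data will show, and neither mentions the diet. In Data Management, breath test scores and the symptom questionnaire "will be compared pre- and post-treatment to determine the efficacy of the supplement therapy". In Intended Use of the Data: "The data collected from this investigation will be used to determine the efficacy of the proposed supplement therapy". The next sentence there provides that, if the therapy proves efficacious, the results will go into print and digital advertising.

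**The concern.** The aim and the announced conclusion name different interventions. Read at face value, Data Management and Intended Use promise a finding about the supplements, while the study tests supplements and diet together. A finding about the supplements alone needs a comparison in which the diet is held constant, and this protocol has none.

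What is at stake is the claim the trial may make, not how it is run. Because Intended Use links a finding of efficacy directly to advertising, loose wording at this point has a practical consequence: nothing in the section limits the advertised result to the combination that patients were given.

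**Working it through.** The protocol gives no figure to reproduce for this point. The check is a comparison of sections, followed by a short identification argument.

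**Step 1. What each section names.**

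| Protocol section | Function | Supplements | Diet |
|---|---|---|---|
| Study Synopsis | aim | yes | yes |
| Objectives | aim | yes | yes |
| Data Management | what the comparison determines | yes | not mentioned |
| Intended Use of the Data | what the data determine | yes | not mentioned |

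**Step 2. Does the term supplement therapy already include the diet?** The informative uses are those that set the term against the diet. There are two:
- Study Synopsis: "After administration of the supplement therapy and adherence to a low FODMAP diet (8 weeks), the lactulose breath test will be repeated". The two are joined as separate items.
- Study Procedures, Visit 0: the investigator "will review the supplement therapy (Supplement Overview - Appendix C) and low FODMAP diet (Low FODMAP Handout - Appendix D"). Each has its own appendix.

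Both point to the products as distinct from the diet. In the same vein, Visits 1 and 2 ask about compliance with the supplements and with the diet as two named items, although the label used there is supplement protocol.

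**Step 3. What the design can identify.** For a given outcome, write the expected pre/post change as

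Δ = S + D + I + B

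where S is the effect of the supplements, D the effect of the diet, I any joint effect, and B the change that would have occurred with neither. B covers natural course, open-label expectation, and regression to the mean, since patients enter on a positive breath test that is then repeated as an outcome. Rearranged,

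S = Δ − (D + I + B).

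Every patient is assigned both components over the same 8 weeks and there is no control, so the design estimates Δ but supplies no estimate of D, I or B.
- If D + I + B = 0, then S = Δ.
- If D + I + B = Δ, then S = 0.

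Both cases predict the same data. More than 10 patients would narrow the interval around Δ and leave the split as open as before.

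**Step 4. Does anything else in the protocol supply the split?**
- There are two outcomes, and the questionnaire is completed at baseline, at about week 4 and at the end. By week 4 both components are in use, so the same equation applies to each outcome and each interval.
- Compliance is reported separately for each component, but by the patient and without randomisation. Comparing better and worse compliers would not isolate S.
- A concurrent diet-only group would have expected change D + B. Subtracting it from Δ gives S + I, the effect of adding supplements to the diet. The protocol has no such group.

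**The case against.** The strongest reply is that supplement therapy is shorthand for the whole package. The title and the Background speak of a supplement-based therapy without mentioning the diet. Appendix C, to which Visit 0 ties the term, carries a dietary instruction ahead of its product tables. The Objectives, which govern what is tested, name the combination. On this reading the two later sections are merely loose.

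That reading is possible, and part of the evidence against it is weaker than it looks. Exclusion criteria 4 and 5 ("Major drug-supplement interactions between essential medication and the proposed supplement therapy" and "A known allergy to one or more of the ingredients in the supplement therapy") use the term for products, as does the Risk/Safety sentence on reactions to ingredients. But drug interactions, allergies and ingredient reactions would concern the products under either reading, so these uses do not discriminate. Only the Synopsis and Visit 0 do. They are enough to show that the term is not defined to include the diet, and a statement of what the data will establish should not depend on a charitable reading.

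It can also be said that an uncontrolled pilot is a disclosed choice and that the harm is conjectural. The first is true and is not what is criticised here. The second is partly true: the risk lies in what the text permits, not in anything it announces.

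**Conclusion.** The inconsistency is real and should be corrected. Both statements of aim name supplements plus diet; both statements of what the data will determine name the supplement therapy only. Attribution to the supplements apart from the diet is outside what a single open-label arm assigned both components can deliver. No numerical share can be given for the supplements, because the design estimates only the total change. Procedures, data and sample size are unaffected.

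The conclusion rests on two things: that both components are assigned to every patient over the same 8 weeks without a control, which the protocol states, and that supplement therapy is at best ambiguous, which the Synopsis and Visit 0 show.

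A reader might infer more than the document supports:
- *That the sponsor plans to advertise the supplements without the diet.* Intended Use does not say so; it only fails to exclude it.
- *That supplements, diet and background influences are all absent beforehand and all present afterwards in every patient.* Neither the criteria nor the eligibility checklist excludes earlier low FODMAP dieting, no washout is required, and medically necessary supplements may continue. Being assigned together is also not the same as being adhered to together. The argument needs only joint assignment without a comparator.
- *That the aims in the Synopsis and Objectives must be rewritten.* They name the combination correctly, and the lack of a control is stated openly in the Synopsis.

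**What to change.** 1. In Data Management and in Intended Use of the Data, replace *the (proposed) supplement therapy* with *the supplement protocol combined with a low FODMAP diet*.
2. In Intended Use, keep the sentence that makes advertising conditional on efficacy, since it is the only condition the section puts on advertising. Add after it: *Any report or advertising will describe the result as an uncontrolled pre/post change under the combined programme and will attribute no effect to the supplements alone.*
3. Leave the aims in the Synopsis and Objectives unchanged.

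The cost is one short amendment, which the protocol requires to go to the IRB for approval before use. No visit, procedure or sample size changes. The downside for the sponsor is a weaker product claim.
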